2.4.4.4 Multiplicity issues

Statistical significance will be claimed for the primary efficacy endpoint (time to first clinical relapse after randomization) of the double-blind period only, if the computed p-value from this primary analysis with a 2-sided log-rank test is <0.05 .

Efficacy analyses performed for primary and secondary endpoints of the open-label period are of exploratory intent in principle to better understand treatment effects of teriflunomide monotherapy beyond the double-blind period in the pediatric population. The step-down testing procedure for controlling multiplicity will not be applied to these exploratory analyses in the open-label period.

2.4.5 Analyses of safety data

The summary of safety results will be presented by treatment patients actually received in the double-blind and open-label period (placebo/teriflunomide and teriflunomide/teriflunomide) and overall treatment group. Baseline values of the double-blind period will be used as the baseline in the safety analysis for the open-label CSR, unless otherwise noted.

General common rules

All safety analyses will be performed on the safety population as defined in [Section 2.3.3](#), unless otherwise specified, using the following common rules:

- Safety data in patients who do not belong to the safety population will be listed separately.
- The baseline value is defined as the last available value before the first intake of IMP in the double-blind period.
- The potentially clinically significant abnormality (PCSA) values are defined as abnormal values considered medically important by the Sponsor according to predefined criteria/thresholds based on literature review and defined by the Sponsor for clinical laboratory tests, vital signs, and ECG (PCSA version dated May 2014 [[Appendix A](#)]).
- PCSA criteria will determine which patients had at least 1 PCSA during the treatment-emergent adverse event period, taking into account all evaluations performed during the treatment-emergent adverse event period, including nonscheduled or repeated evaluations. The number of all such patients will be the numerator for the on-treatment PCSA percentage.
- The treatment-emergent PCSA denominator by group for a given parameter will be based on the number of patients assessed for that given parameter in the treatment-emergent adverse event period by treatment group on the safety population.
- For quantitative safety parameters based on central laboratory/reading measurements, descriptive statistics will be used to summarize results and change from baseline values of the double-blind period by visit and treatment group. Summaries will include the endpoint value and/or the minimum and maximum value. The endpoint value is commonly defined as the value collected at the same day/time of the last administration of IMP in the open-label period. If this value is missing, this endpoint value will be the closest value prior to the last dose intake.
- All the values including unscheduled measurements will be assigned to the appropriate safety analysis visit window. In the presence of multiple measurements of the same test in the same window (see [Table 6](#) and [Table 7](#) in [Section 2.5.3](#)), the one closest to the targeted visit date will be used for the by-visit summaries.
- The analysis of the safety variables will be essentially descriptive and no systematic testing is planned.

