2.1 ANALYSIS ENDPOINTS

2.1.1 Demographic and baseline characteristics

The baseline value is defined as the last available value before the first intake of IMP in the double-blind period, unless otherwise specified.

All baseline safety and efficacy parameters (apart from those listed below) are presented along with the on-treatment summary statistics in the efficacy and safety sections (see [Section 2.4.4](#) and [Section 2.4.5](#)).

Demographic characteristics

Demographic variables are gender (Male, Female), race (Caucasian/white, Black, Asian/Oriental, other), ethnicity (Hispanic or Latino, Not Hispanic or Latino), region (definition of the regions are provided in [Section 2.5.5](#)), age in years at study consent of the double-blind period (quantitative and qualitative variable: <13, and ≥ 13 years), pubertal status, Tanner staging.

Medical or surgical history

Medical (or surgical) history includes concurrent illnesses, detailed neurological history and detailed vaccination history.

This information will be coded using the version of Medical Dictionary for Regulatory Activities (MedDRA) currently in effect at Sanofi at the time of database lock.

Disease characteristics at baseline

Specific disease history includes the following:

- Time since first diagnosis of Multiple sclerosis (MS) relative to randomization (in years)
- Time since first symptoms of MS relative to randomization (in years)
- Time since most recent relapse onset relative to randomization (in months)
- MS type (relapsing remitting, progressive relapsing)
- Number of relapses experienced within past 1 year (quantitative variable and qualitative variable: 0, 1, 2 and ≥ 3)

- Number of relapses experienced within past 2 years (quantitative variable and qualitative variable: 0, 1, 2, 3 and ≥ 4)
- Number of relapses experienced overall (quantitative variable and qualitative variable: 0, 1, 2, 3 and ≥ 4)
- With previous MS medication in the last 2 years (Yes, No)
- Total number of any events since onset of MS (0, 1, 2-5 and >5) and the subtype (Non encephalopathic Central nervous system (CNS) clinical events, Acute Disseminated Encephalomyelitis (ADEM), other event).

Vital signs

Vital signs at baseline as well as extension baseline (defined as the last available value before the first intake of IMP in the open-label extension period) are weight in kilograms (quantitative variable and qualitative variable: ≤ 40 , >40), height in cm, Body Mass Index (BMI) in kg/m^2 .

Other

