Long-term safety of teriflunomide exposure will also be analyzed by including all teriflunomide exposure, ie, from randomization in the double-blind period in the teriflunomide group and from start in the open-label period in the placebo group, for the complete study population analyzed in one overall group. Key safety analyses on TEAEs, SAEs, TEAEs leading to treatment discontinuation and AESIs.

Safety Subgroup Analysis

Safety subgroup analyses will be performed for key tables of TEAEs/SAEs/AESIs and TEAEs leading to treatment discontinuation during the treatment-emergent adverse event period in the open-label period by:

- Intrinsic factors
 - Age group at study consent of the double-blind period (<13, ≥13 years)
 - Gender
 - Race
 - Pubertal status (at study consent, and at disease onset)
 - Baseline weight group in the double-blind period (≤40, >40 kgs)
 - MS subtypes (relapsing-remitting MS, other forms)
 - High disease activity at baseline (defined as 2 or more relapses in the past year of screening, and 1 or more Gadolinium enhancing lesions on baseline MRI of the double-blind period) (Yes, No)
- Extrinsic factors
 - Region (as defined in [Section 2.5.5](#)).

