2.4.5.3 Analyses of laboratory variables

The summary statistics (including number, mean, median, Q1, Q3, standard deviation, minimum and maximum) of all laboratory variables (central laboratory values and changes from baseline) will be calculated for each visit or study assessment (baseline, each postbaseline time point, last on-treatment and/or minimum and maximum value during the treatment-emergent adverse event period) by treatment group. Mean changes from baseline with the corresponding standard error will be plotted over time (at same time points) in each treatment group for laboratory parameters of primary interest. This section will be organized by biological function.

PCSA will be assessed based on age group at each visit. After subjects turn to be adult, the adult criteria will be applied. The incidence of PCSAs (list provided in [Appendix A](#)) at any time during the treatment-emergent adverse event period will be summarized by biological function and treatment group whatever the baseline level and/or according to the following baseline status categories:

- Normal/missing.
- Abnormal according to PCSA criterion or criteria.

The proportion of patients with key PCSA values at any time during the treatment-emergent adverse event period will also be displayed by duration of exposure for each treatment group.

For parameters for which no PCSA criteria are defined, similar table(s) using the normal range will be provided.

A listing of patients with at least one post-baseline PCSA will be provided and will display the whole profile over time at any time of all parameters of the corresponding biological function. In this listing, baseline, endpoint value and individual values will be flagged when lower or higher than the lower or upper laboratory limits and/or when reaching the absolute limit of abnormality criteria.

Drug-induced liver injury

The liver function tests, namely AST, ALT, alkaline phosphatase, and total bilirubin, are used to assess possible drug-induced liver toxicity. The proportion of patients with PCSA values at any postbaseline visit by baseline status will be displayed by treatment group for each parameter. The proportion of patients with PCSA values at any postbaseline visit will also be displayed by duration of exposure for each treatment group.

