When the date of the first IMP administration is missing, all adverse events that occurred on or after the day of randomization should be considered as treatment-emergent adverse events. The exposure duration should be kept as missing.

The last dose intake should be clearly identified in the case report form and should not be approximated by the last returned package date.

Handling of missing assessment of relationship of adverse events to investigational medicinal product

If the assessment of the relationship to IMP is missing, then the relationship to IMP has to be assumed and the adverse event considered as such in the frequency tables of possibly related adverse events, but no imputation should be done at the data level.

Handling of missing severity of adverse events

If the severity is missing for 1 of the treatment-emergent occurrences of an adverse event, the maximal severity on the remaining occurrences will be considered. If the severity is missing for all the occurrences, a “missing” category will be added in the summary table.

Handling of potentially clinically significant abnormalities

If a patient has a missing baseline he will be grouped in the category “normal/missing at baseline.”

For PCSAs with 2 conditions, one based on a change from baseline value of the double-blind period or a normal range and the other on a threshold value, with the first condition being missing, the PCSA will be based only on the second condition.

For a PCSA defined on a threshold and/or a normal range, this PCSA will be derived using this threshold if the normal range is missing; eg, for eosinophils the PCSA is >0.5 GIGA/L or $>ULN$ if $ULN \geq 0.5$ GIGA/L. When ULN is missing, the value 0.5 should be used.

Measurements flagged as invalid by the laboratory will not be summarized or taken into account in the computation of PCSA values.

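### Open-label laboratory and vital-sign changes, change-based PCSAs and baseline strata for placebo/teriflunomide patients are measured from before the placebo period, so placebo-time change is mixed with change on drug

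*SAP*

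**What the plan says.** SAP 2.4.5 sets the baseline for the open-label safety analysis: "Baseline values of the double-blind period will be used as the baseline in the safety analysis for the open-label CSR, unless otherwise noted". Its common rules define it as follows: "The baseline value is defined as the last available value before the first intake of IMP in the double-blind period". Quantitative parameters follow the same rule: "descriptive statistics will be used to summarize results and change from baseline values of the double-blind period by visit and treatment group". SAP 2.5.2 carries it into PCSAs with two conditions, "one based on a change from baseline value of the double-blind period or a normal range and the other on a threshold value". Sections 2.4.5.3 to 2.4.5.5 (laboratory, vital signs, ECG) make no exception for either sequence group.

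Patients meeting a PCSA in the open-label treatment-emergent period are labelled as on-treatment: "The number of all such patients will be the numerator for the on-treatment PCSA percentage". Incidence is also to be shown by baseline status, normal or missing against "Abnormal according to PCSA criterion or criteria".

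Two other passages recognise that placebo patients start the drug later. SAP 2.1.1 defines an "extension baseline (defined as the last available value before the first intake of IMP in the open-label extension period", but uses it only to describe weight, height and BMI. The long-term safety paragraph of SAP 2.4.5.1 counts teriflunomide exposure "from start in the open-label period in the placebo group".

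**The concern.** A change from baseline is read as a change since the drug was started. For placebo/teriflunomide patients it would instead be the change since placebo was started, in adolescents who are still growing. A hemoglobin fall or blood pressure rise that developed on placebo and persists would appear as an on-treatment event. A laboratory value that became abnormal on placebo would appear in the normal-at-baseline stratum.

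This matters because several adult findings in protocol 3.1.2.2 are changes from a pre-drug value: a mean rise in blood pressure, a 20% to 30% fall in mean uric acid, and a white-cell fall during the first 6 weeks. In the open-label report, placebo/teriflunomide is the group in which effects of starting the drug could be seen, and the planned tables blur them.

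**Working it through.** **1. Which outputs use the baseline** (SAP 2.1.4.1, 2.4.5, 2.5.2 and Appendix A)

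| Output | Uses the double-blind baseline? |
|---|---|
| By-visit change summaries and plots | Yes |
| PCSAs with a change condition: SBP, DBP, heart rate, weight, hemoglobin fall, QTc; in adults also creatinine, PR, QRS | Yes |
| Normal/missing versus abnormal strata | Yes |
| Overall incidence of threshold-only PCSAs (ALT, neutrophils, amylase, lipase; paediatric creatinine) | No |
| TEAE, SAE and AESI counts (onset, worsening or becoming serious in the open-label period) | No |
| Long-term analysis (TEAEs, SAEs, discontinuations, AESIs) | No |

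**2. How far the baseline precedes the first teriflunomide dose**

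The plan gives no figure for this. Inputs from SAP 1.3 and protocol 5.1: 60% placebo relapse at 2 years, 20% discontinuation at 2 years, a double-blind maximum of 96 weeks, and a switch only for a relapse after Week 8.

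- The plan's hazard reproduces: -ln(0.40)/2 = 0.4581 per year, or λ = 0.008780 per week.
- Dropout, assumed exponential: -ln(0.80)/2 = 0.1116 per year, or g = 0.002138 per week.
- a = λ + g = 0.010919 per week.

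| Convention | Formula | Mean weeks |
|---|---|---|
| Any relapse ends the period; dropout included | (1 - e^(-96a))/a | 59.5 |
| Any relapse ends the period; no dropout | (1 - e^(-96λ))/λ | 64.9 |
| Relapse after Week 8 only; dropout; among patients entering open label | see below | 67.2 |
| Relapse after Week 8 only; no dropout | 8 + (1 - e^(-88λ))/λ | 69.3 |

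Third row. Among patients still in the trial at Week 8, the share switching at a relapse is (λ/a)(1 - e^(-88a)) = 0.4965, and the share completing 96 weeks is e^(-88a) = 0.3826. The time-weighted sum is 8(0.4965) + (λ/a)[(1 - e^(-88a))/a - 88e^(-88a)] + 96(0.3826) = 59.10. The mean is 59.10/(0.4965 + 0.3826) = 67.2 weeks, and 0.3826/0.8791 = 44% of entrants are at the full 96 weeks. Switches for high MRI activity are not modelled; they would shorten the interval.

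**3. Direction, using weight** (growth rates are assumptions, not document figures)

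Gain before the first teriflunomide dose = (1 + r)^(weeks × 7/365.25) - 1. Loss from open-label entry needed to reach 5% below the double-blind baseline = 1 - 0.95/(1 + gain).

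| Growth per year | Gain, 65 weeks | Gain, 96 weeks | Loss needed, 65 weeks | Loss needed, 96 weeks |
|---|---|---|---|---|
| 1% | 1.2% | 1.8% | 6.2% | 6.7% |
| 3% | 3.8% | 5.6% | 8.4% | 10.0% |
| 5% | 6.3% | 9.4% | 10.6% | 13.2% |
| 8% | 10.1% | 15.2% | 13.7% | 17.5% |

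The adult table in Appendix A flags a gain of 5% or more. At 3% growth or above over 96 weeks, that condition is already met at open-label entry, and it counts once the patient is assessed as an adult. The paediatric table flags only a loss of 5% or more, so the same growth hides true loss on drug.

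**4. Direction, using adolescent systolic pressure**

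The PCSA needs both 119 mmHg or more and a rise of at least 20 mmHg. Simulation with assumed values: mean 108, between-patient SD 8, a 96-week gap, one open-label year and no drug effect. One-visit rates, double-blind baseline versus extension baseline:

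| Drift per year | Within-patient SD 6 | SD 8 | SD 10 |
|---|---|---|---|
| 0 mmHg | 0.5% vs 0.5% | 2.1% vs 2.1% | 4.6% vs 4.6% |
| 2 mmHg | 3.0% vs 1.2% | 7.0% vs 4.1% | 10.7% vs 7.5% |
| 3 mmHg | 6.3% vs 1.8% | 11.3% vs 5.3% | 15.4% vs 9.2% |

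With no drift the choice of baseline makes no difference. With drift, the double-blind baseline gives the higher rate.

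**The case against.** A common baseline is a coherent choice for a descriptive long-term report. Results are split by sequence group, no systematic testing is planned, and the SAP calls the open-label data non-controlled and supportive. SAP Table 7 has a transition row, so group-level drift up to open-label entry can be seen beside later visits. The laboratory PCSA listing shows each patient's profile over time. Starting the drug is assessed against a concurrent control in the double-blind report, which is stronger evidence than an uncontrolled before-and-after view.

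All of that stands, and it makes this an improvement rather than a flaw that threatens a conclusion. But the transition row shows drift only at group level; it does not reclassify a patient's change-based PCSA or baseline stratum. The profile listing leaves the correction to be made by eye.

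A reader might go further and infer that open-label safety rates in general are inflated against teriflunomide, or that the long-term analysis lacks a matching baseline. The documents support neither. The long-term paragraph lists only adverse event outputs, which use no laboratory or vital-sign baseline. Threshold-only PCSA incidence does not depend on the baseline, and it covers the liver, pancreatic and neutrophil thresholds that the protocol monitors specifically. Blood pressure drift alone does not trigger a PCSA, because the absolute threshold must also be met. For paediatric weight, growth hides events rather than adding them.

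**Conclusion.** The point holds within limits, as a low-cost improvement. For placebo/teriflunomide patients (up to the 55 randomized to placebo), by-visit changes, change-conditioned PCSAs and baseline strata include time on placebo: up to 96 weeks, and roughly 59 to 69 weeks on average. The average rests on the planning hazard, exponential dropout where dropout is included, and no MRI switches. It measures elapsed time, not bias.

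The size of any misclassification cannot be derived from the documents, which give no growth or variability figures; the weight and blood pressure results are illustrations under stated assumptions. The error can go in either direction. For teriflunomide/teriflunomide patients the planned baseline is the right one.

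**What to change.** For placebo/teriflunomide only, add laboratory and vital-sign change summaries, baseline-status splits and change-based PCSAs measured from the extension baseline (the last value before the first open-label dose, as SAP 2.1.1 defines it). Keep the existing double-blind-baseline tables for both groups.

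No new data collection is needed. Vital signs are scheduled at transition, and routine laboratories are too unless they were done within the previous 4 weeks. The cost is more tables.

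Two limits should be stated with the tables. ECG, TSH and immunoglobulins have no scheduled transition assessment, and the double-blind end-of-treatment visit is not required for patients who switch early, so some will lack a recent value; exclude or footnote these parameters. Re-baselining also does not remove growth after open-label entry.

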EOT = end of treatment (EOT= First visit after last study drug intake), EDSS = expanded disability status scale, FS = functional score, BVMTR = brief visuospatial memory test-revised, SDMT=symbol digit modalities test, MRI = magnetic resonance imaging, PK = pharmacokinetic

- a Recommended windows: The window for obtaining biological samples at any given visit will be ±7 days. All other treatment period assessments should be completed within ±7 days of the scheduled visit date relative to the randomization visit. Post drug elimination follow-up visits should be ±7 days of scheduled visit relative to end of treatment.
- b Randomization visit up to 28 days from signing of informed consent.
- c End-of-treatment and premature discontinuation visit. This visit does not need to be performed when the patient switches to the open label period after a confirmed relapse or high MRI activity (as per protocol criteria). The drug elimination procedure must be initiated at this visit if applicable.

- d* For discontinuing treatment, 2 post drug elimination follow up visits should be scheduled 2 weeks and 4 weeks after study medication discontinuation and initiation of the drug elimination procedure. All patients who prematurely and permanently discontinue study medication will be asked to continue until the planned end of double-blind period.
- e* Re-consent must follow any RAP confirmed MS relapse for continuing in study when occurrence during PK run-in, for switching into open-label period when occurrence after PK run-in.
- f* To be prescribed at Visit 1 and report checked at Visit 2. MRI scan performed within 6 weeks prior to randomization can be used as the baseline MRI if performed according to the operations manual and accepted by the central reader.
- g* During the adverse event reporting process, specific questions about pulmonary symptoms and peripheral neuropathy symptoms will be asked. (Patients will be instructed to alert the treating physician of symptoms suggestive of immunodeficiency).

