1.4 STUDY PLAN

The study design is briefly described in the following graphical presentation:

R: Randomization

Note: An optional additional extension period with teriflunomide is offered to young patients when they complete the study, to provide treatment until they are 18 years old and/or can switch to commercial product, whichever comes first.

Table 1 - Study schedule for the double-blind period

Variable	Visit
Brain MRI	Screening, Weeks 24, 48, 72 and Week 96/end of treatment (EOT) ^a visit, Week 36 if necessary
EDSS	Screening, randomization, Weeks 24, 48, 72, Week 96/EOT ^a visit, and unscheduled relapse visits
SDMT	Randomization, Weeks 24, 48, 72, and Week 96/EOT ^a visit,
Cognitive Battery Test	Randomization and EOT ^a visit
Clinical Laboratory	Screening, randomization, every 4 weeks up to 24 weeks and then every 6 weeks up to the Week 96/EOT ^a
Vital signs	Screening, randomization, Weeks 4, 8, 12, 24, and every 12 weeks up to Week 96/EOT ^a visit
ECG	randomization, Week 96/EOT ^a and after EOT ^a if abnormality
Immunoglobulins and TSH	Randomization, Weeks 24, 48, 72 and Week 96/EOT ^a visit
PK	Weeks 2, 3, 4, 8, 12, 24, 36 and Week 96/EOT ^a visit
Physical examinations	Screening, randomization, Weeks 12, 24, and every 12 weeks up to Week 96/EOT ^a visit
Tanner assessment	Randomization, at Week 24, 48, 72, and at Week 96/EOT ^a for all patients (until complete sexual maturity).

^a Patients who complete the double-blind treatment period or who prematurely discontinue, should complete EOT visit.

Table 2 - Study schedule for the open-label period

Variable	Visit
Brain MRI	Weeks 48, 96, 144 and Week 192/end of treatment (EOT) ⁰ visit
EDSS	Weeks 24, 48, 72, 96, 120, 144, 168, Week 192/EOT ⁰ visit, and unscheduled relapse visits
SDMT	Weeks 24, 48, 72, 96, 120, 144, 168, Week 192/EOT ⁰ visit
Cognitive Battery Test	Week 96 and Week 192/EOT ⁰ visit
Clinical Laboratory	Transition, Weeks 4, 12, and then every 12 weeks up to the Week 192/EOT ⁰
Vital signs ^b	Transition, Weeks 4, 8, 12, and then every 12 weeks up to the Week 192/EOT ⁰
ECG	Week 192/EOT ⁰ and after EOT ⁰ if abnormality on EOT or ECG could not be performed at EOT (in exceptional circumstances).
Immunoglobulins and TSH	Week 96 and Week 192/EOT ⁰ visit
PK	Weeks 2, 3, 4, 8, 12, 24, 36 and Week 192/EOT ⁰ visit
Physical examinations	Weeks 12, 24, and then every 24 weeks up to the Week 192/EOT ⁰

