2.1.4.5 Electrocardiogram variables

A standard 12-lead ECG will be performed at randomization, EOT in the double-blind period and EOT in the open-label period and will be evaluated centrally.

ECG parameters include heart rate, PR interval, QRS interval, QT, and corrected QTc (QTc interval calculated by Bazett's method) and QTcF (QTc interval calculated by Fridericia's method).

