Week (W) ^a	W102	W108	W114	W120	W126	W132	W138	W144	W150	W156	W162	W168	W174	W180	W186	W192/ EOT ^{b, u}	EOT +2W	EOT +4W	Relapse visit
Visit number ^r	20	21	22	23	24	25	26	27	28	29	30	31	32	33	34	35	36 ^c	37 ^c	
Treatments																			
Concomitant medications	X	X	X	X	X	X	X	X	X	X	X	X	X	X	X	X	X	X	X
Dispense study drugs/IVRS call		X		X		X		X		X		X		X		X ^t			
Accountability/co compliance		X		X		X		X		X		X		X		X			
Teriflunomide PK sampling ^k																X	X ^l	X ^l	

EOT = end of treatment (EOT= First visit after last study drug intake), EDSS = expanded disability status scale, FS = functional score, BVMTR = brief visuospatial memory test-revised, SDMT=symbol digit modalities test, MRI = magnetic resonance imaging, PK = pharmacokinetic.

- a The open label period starts by the transition visit. It is recommended that there is no time gap between the 2 periods, or as short as possible and if possible less than 2 weeks. In case of start of the open label period at the end of the 96 weeks of the double-blind period, the transition visit will generally coincide with the EOT visit of the double-blind period. Recommended windows: The window for obtaining biological samples at any given visit will be ±7 days. All other treatment period assessments should be completed within ±7 days of the scheduled visit date relative to the transition visit. Post drug elimination follow-up visits should be ±7 days of scheduled visit relative to end of treatment.
- b End-of-treatment and premature discontinuation visit.
- c For patients discontinuing treatment, 2 post drug elimination follow up visits should be scheduled 2 weeks and 4 weeks after study medication discontinuation and initiation of the drug elimination procedure. When applicable patients who prematurely and permanently discontinue study medication will be asked to continue until the planned end of double-blind period (ie, 96 weeks after randomization).
- d Re-consent before starting open-label period and after confirmed MS relapse and when patients turn adults as per local regulations.
- e During the adverse event reporting process, specific questions about pulmonary symptoms and peripheral neuropathy symptoms will be asked. (Patients will be instructed to alert the treating physician of symptoms suggestive of immunodeficiency).

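### SAP 2.4.5 lets the ECG endpoint value fall back to a pre-open-label recording when the end-of-treatment ECG is dated after the last dose, and this conflicts with SAP 2.4.5.5

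*SAP*

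**What the plan says.** SAP 2.4.5 (general common rules) sets the scope: "For quantitative safety parameters based on central laboratory/reading measurements, descriptive statistics will be used to summarize results". The summaries may include an endpoint value: "The endpoint value is commonly defined as the value collected at the same day/time of the last administration of IMP in the open-label period". The fallback is: "If this value is missing, this endpoint value will be the closest value prior to the last dose intake". ECGs are evaluated centrally, so they are in scope.

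On the schedule, SAP 2.1.4.5 says: "A standard 12-lead ECG will be performed at randomization, EOT in the double-blind period and EOT in the open-label period". The ECG row of the open-label flow chart (SAP Appendix C; Protocol 1.3 and 1.4) is empty until Week 192/EOT. SAP Table 2 adds a later ECG only "if abnormality on EOT or ECG could not be performed at EOT (in exceptional circumstances".

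The Appendix C legend gives: "EOT = end of treatment (EOT= First visit after last study drug intake". On the double-blind EOT visit, Protocol 1.2 footnote c says: "This visit does not need to be performed when the patient switches to the open label period after a confirmed relapse". The same exemption applies to a switch for high MRI activity.

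SAP 2.4.5.5 (ECG variables) does not mention an endpoint value. It lists baseline, each postbaseline time point, a last on-treatment value and/or the extremes, and refers to the treatment-emergent adverse event (TEAE) period. SAP 2.1.4 runs that period to 28 days after the last open-label dose, or to the first optional-extension dose if earlier.

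**The concern.** The endpoint rule looks only at or before the last dose, while the one scheduled open-label ECG belongs to a visit defined as coming after it. When the two dates differ, the rule rejects the only recording that describes open-label treatment and replaces it with an older one, with no floor at the first open-label dose. The resulting row of heart rate, PR, QRS and QTc would be labelled as an end-of-open-label result but contain pre-open-label data for those patients. Where the substitute is the baseline recording itself, the error is toward no change, which is the wrong direction for a safety summary.

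**Working it through.** No figure in the plan needs reproducing. The check is one of dates.

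Inputs:
- Eligible values: on the day of the last open-label dose, or the nearest earlier one (SAP 2.4.5).
- Scheduled ECGs: randomization, double-blind EOT, open-label EOT (SAP 2.1.4.5).
- Baseline: last value before the first double-blind dose (SAP 2.4.5), normally the randomization ECG.
- Double-blind EOT visit: not required for patients who switch early (Protocol 1.2 footnote c and 10.1.3.4).
- TEAE period: up to 28 days after the last dose (SAP 2.1.4).

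Results, assuming no unscheduled open-label ECG:

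| Patient | Literal SAP 2.4.5 rule | SAP 2.4.5.5 read as the TEAE period |
|---|---|---|
| EOT ECG on the last-dose day | EOT ECG | EOT ECG |
| EOT ECG at least 1 day later; completed the double-blind period | Double-blind EOT ECG | EOT ECG, if within 28 days and before any extension dose |
| EOT ECG at least 1 day later; early switcher with no double-blind EOT ECG | Randomization ECG | As above |
| ECG not possible at EOT, done at a later visit | Excluded; same fallback as rows 2 and 3 | Delayed ECG, if within the TEAE period |

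Age of the substitute for a patient who stays until 192 weeks after randomization:
- Row 2: 192 − 96 = 96 weeks.
- Row 3: 192 − 0 = 192 weeks. The endpoint equals baseline, so change = baseline − baseline = 0 whatever the drug does.

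For placebo/teriflunomide patients, either substitute predates any teriflunomide.

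For row 4, follow-up visits are planned 2 and 4 weeks after stopping, each ±7 days. Counted from the last dose, the first falls no later than day 14 + 7 = 21, inside the 28 days. The second can fall as late as day 28 + 7 = 35, outside them.

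The SAP does not settle which column applies:
- For the TEAE reading: SAP 2.1.4.2 counts on-treatment deaths over the TEAE period, and SAP 2.4.5 does the same for the on-treatment PCSA percentage.
- Against it: the treatment epoch in SAP 2.1.4 ends at the last dose, and the last during-treatment MRI in SAP 2.4.4.2.3 is in general one before treatment ends.
- Protocol 11.4.5 lists an endpoint value for ECG, and SAP 2.4.5 holds the only written derivation of one.
- SAP Table 7 has no ECG window.

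**The case against.** The strongest reply is that the ECG section has its own wording. If *last on-treatment* in SAP 2.4.5.5 means the TEAE period, an EOT ECG within 28 days counts and a double-blind or randomization ECG cannot. That reading is reasonable and stands as a possibility, but the term is undefined and the common rule points the other way, so two programmers could derive different values.

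The second reply is timing. A reader might infer that the ECG endpoint always falls back. The documents do not support that: a same-day value qualifies, Protocol 9.11.1 (Table 3) lists the EOT PK sample as pre-dose, and Protocol 7.1.1 has the tablet taken at the site after such samples. Protocol 10.1 starts elimination on the day of stopping or the next day. These passages allow EOT on the last-dose day, which itself sits badly with the EOT definition. The next-day option and the delayed ECG remain exposed.

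Three further inferences also go too far:
- That a drug effect would be hidden. The EOT ECG still enters the by-visit summary, the TEAE-period extremes and, when it falls within the TEAE period, the PCSA counts. The safety analysis is descriptive, with no systematic testing planned.
- That every early switcher is affected. A zero change also needs an EOT ECG after the last-dose day, the 2.4.5 reading, and no double-blind EOT ECG. That visit is not required, but it is not forbidden either.
- That TSH and immunoglobulins share the fault. Their own text (SAP 2.4.5.3 and 2.4.7) asks for summaries at each assessment and names no endpoint value.

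**Conclusion.** The endpoint rule is wrong as written, with minor severity. Followed literally, it can return a double-blind or randomization ECG as the open-label endpoint, and in the second case it forces a zero change. It also conflicts with SAP 2.4.5.5.

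The effect is limited to one descriptive row, the endpoint or last-value ECG summary. It arises only for patients whose EOT ECG is dated after the last dose, and only if the SAP 2.4.5 wording governs. The documents give no distribution for the gap between last dose and EOT ECG, so the share of patients affected cannot be derived. The conclusion assumes that no unscheduled open-label ECG on or before the last dose supplies a later eligible value.

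**What to change.** Replace the endpoint sentences in SAP 2.4.5 with one definition, and use the same term in 2.4.5.5:

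- The endpoint (last on-treatment) value is the last value after the first open-label dose and within the TEAE period, up to and including the EOT assessment.
- An EOT ECG that could not be done at EOT and was delayed to a follow-up visit counts as the EOT assessment. State whether it still counts if that visit falls beyond day 28, and flag such values, since elimination may have begun.
- If there is no such value, the endpoint is missing. No value from before the first open-label dose is carried in.

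Report the number of patients contributing to the row. The sponsor should also reconcile the EOT definition with the pre-dose EOT PK sample, so that the date relation between last dose and EOT is clear. The cost is one SAP sentence and a small change to the derivation program; no new data are needed.
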